### 12.2.2 Duration of Response (Part 2A and Part 2B)

Duration of response (DOR) for any confirmed RECIST CR or PR will be measured from the date of the first occurrence of a response until the first occurrence of PD per RECIST. DOR will be summarized as a time to event variable. For patients who continue treatment post-progression, the first date of progression will be used for the analysis. Any patients with an ongoing response will be censored at the date of the last post-baseline scan. The Kaplan-Meier methodology will be used to summarize DOR. If able to be estimated, the 50th (median) together with a 95% Confidence Interval (CI), will be presented. The number of patients with PD events and the number of censored patients will also be presented.

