11.2.4.2.2 Tumor Marker (CA-125) Response Rate Based on GCIG CA-125 Criteria (Part 2)

Only patients with elevated level as baseline will be used for this analysis. The incidence of patients with a response (i.e., at least 50% reduction from baseline which is confirmed at a second post-baseline value) in tumor marker CA-125 will be summarized. The time to CA-125 may also be summarized with Kaplan-Meier methodology where the time to CA-125 is defined as duration between the date of first study drug to the date of the first CA-125 response value (at least 50% reduction). If the patient does not have a response they are censored at the last date of cancer antigen measurement.

11.2.4.2.3 *Progression-free Survival (PFS) (Part 2)*

PFS will be calculated as 1+ the number of days from the date of first dose of study drug to disease progression or death, due to any cause, whichever occurs first. Patients without a documented event of progression will be censored on the date of their last adequate tumor assessment (i.e., radiologic assessment) or date of first dose of study drug if no tumor assessments have been performed. PFS will be summarized using Kaplan-Meier methodology.

11.2.4.2.4 *Duration of Response - Secondary Endpoint (Part 2)*

Duration of response for CR and PR, a secondary endpoint in Part 2, will be measured from the date that any of these best responses is first recorded until the first date that PD is objectively documented. Duration of response will be summarized using descriptive statistics (N, mean, standard deviation, median, minimum, and maximum) as well as categorically.

11.2.4.2.5 *Overall Survival (Part 2B)*

Overall survival is defined as the 1+ the number of days from the date of first dose of study drug to death, due to any cause. Patients without a documented event of death will be censored on the date of their last visit. Overall survival will be summarized using Kaplan-Meier methodology time from randomization until death from any cause, and is measured in the intent-to-treat population.

11.2.4.2.6 *Evaluation of Antitumor Activity – Secondary Endpoint (Parts 1 and 3)*

No formal statistical analysis of efficacy will be performed in Part 1. For patients with measurable disease, response to treatment according to RECIST Version 1.1 will be reported via descriptive statistics by dose level.

11.2.4.2.6.1 *Changes in Tumor Markers Applicable to Patient's Tumor Type (Part 1 and 3)*

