CT scans are required within 7 days prior to the start of Cycles 3, 5, and 7, and then within 7 days prior to the start of every third cycle of treatment thereafter, beginning with Cycle 10. If an initial CR or PR is noted at Cycle 7 or beyond, confirmatory scans must be performed 4-6 weeks later. In the case of SD, follow-up measurements must have met the SD criteria at least once after study entry at a minimum interval of no less than 6–8 weeks.

Duration of Overall Response

The duration of overall response is measured from the time measurement criteria are met for CR or PR (whichever is first recorded) until the first date that recurrent or PD is objectively documented (taking as reference for PD the smallest measurements recorded since the treatment started).

The duration of overall CR is measured from the time measurement criteria are first met for CR until the first date that recurrent disease is objectively documented.

Duration of Stable Disease

SD is measured from the start of the treatment until the criteria for progression are met, taking as reference the smallest measurements recorded since the treatment started.

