### 12.2.1 Progression-free Survival (Part 2)

PFS will be calculated as 1+ the number of days from the date of first dose of study drug to disease progression or death, due to any cause, whichever occurs first. Patients without a documented event of progression will be censored on the date of their last adequate tumor assessment (i.e., radiologic assessment) or date of first dose of study drug if no tumor assessments have been performed. PFS will be summarized using Kaplan-Meier methodology.

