## **13 STATISTICAL/ANALYTICAL ISSUES**

### **13.1 Handling of Dropouts or Missing Data**

All data will be used to their maximum possible extent but without any imputations for missing data. All time to event endpoints are censored and the rules for deriving the censoring value is described in more detail under each one of the time to event endpoints.

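### Duration of response ends at RECIST progression only, so a responder who dies without documented progression would most naturally be censored

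*SAP*

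**What the plan says.** For patients with a confirmed complete or partial response, SAP 12.2.2 states that DOR "will be measured from the date of the first occurrence of a response until the first occurrence of PD per RECIST". It gives one censoring rule: "Any patients with an ongoing response will be censored at the date of the last post-baseline scan". It reports two categories: "The number of patients with PD events and the number of censored patients will also be presented". SAP 13.1 adds no further rule; it says that "the rules for deriving the censoring value is described in more detail under each one of the time to event endpoints".

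The protocol ends DOR at the same place. Section 11.2.4.2.4 runs it "until the first date that PD is objectively documented", and Appendix A "until the first date that recurrent or PD is objectively documented". Neither names death.

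Progression-free survival (PFS) is defined differently. SAP 12.2.1 counts time "to disease progression or death, due to any cause, whichever occurs first", and the PFS row of SAP Table 1 also names death as an event.

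**The concern.** A responder who dies without documented PD does not fit the DOR text. There is no PD event, and a patient who has died does not literally have an ongoing response. With only two reporting categories and no rule elsewhere, a programmer would most naturally put that patient among the censored, at the last scan. Kaplan-Meier then treats the patient as someone whose response could still have ended in PD later.

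The plan allows for such patients. Protocol Appendix A describes patients who stop treatment because of global deterioration without objective progression. Protocol 9.9 lists death among the events that end Part 2B follow-up scanning.

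At stake is how the DOR median is read. A reader who takes it as time to PD or death, the event set used for PFS, would read a figure that is generally too long for that purpose.

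**Working it through.** The documents state no expected DOR median, event count or precision, so there is no figure of the plan's own to reproduce. The check concerns direction and size.

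**Inputs**
- From the documents: the definitions above, and the 9-week scan interval in Part 2B long-term follow-up (protocol 9.9).
- Assumed: f, the share of responders' first events (PD or death) that are deaths without documented PD, at 0, 5, 10 and 15%; and a PD-or-death median m of 6 to 10 months.
- The nearest figure in the documents is in protocol 3.2.2.1: five deaths among 163 patients, 5/163 = 3.1%. This is not f. It is not limited to responders, all five deaths were attributed to disease progression, and it is not said whether RECIST PD had been documented.

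**Closed form.** With constant hazards h_PD and h_D, f = h_D/(h_PD + h_D). The PD-only median is ln2/h_PD and the PD-or-death median is ln2/(h_PD + h_D), so their ratio is 1/(1-f). Months added are m × (ratio - 1). At the time when half have had PD or died, the PD-only curve reads 0.5^(1-f); this needs only proportional cause-specific hazards.

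| f (assumed) | Ratio of medians | Added, m = 6 months | Added, m = 10 months | PD-only curve at the PD-or-death median |
|---|---|---|---|---|
| 0% | 1.00 | 0 | 0 | 50% |
| 5% | 1.05 | 0.32 | 0.53 | 52% |
| 10% | 1.11 | 0.67 | 1.11 | 54% |
| 15% | 1.18 | 1.06 | 1.76 | 55% |

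These formulas censor at the date of death. SAP 12.2.2 censors at the last scan, so a simulation was run as well.

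**Simulation.** 3,000 trials per setting, 9-weekly scans, an assumed PD-or-death median of 39 weeks and an assumed data cutoff at 52 to 104 weeks. Deaths were either censored at the last scan or counted as events. With 30 responders, the mean Kaplan-Meier median (over trials in which both medians were reached) was, censored versus event:
- f = 3%: 44.4 vs 42.4 weeks
- f = 5%: 45.6 vs 42.3 weeks
- f = 10%: 48.3 vs 41.8 weeks
- f = 20%: 54.0 vs 41.4 weeks

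These gaps need not match the closed form: PD is dated at a scan, death on its day, and a progression followed by death before the next scan counts as a death without documented PD.

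**Where the direction weakens.** With 30 responders and f = 10%, deaths delayed by 13, 26 and 39 weeks gave 48.6 vs 43.6, 48.5 vs 45.3 and 48.5 vs 47.3 weeks. At 39 weeks' delay the censored median was the shorter one in 3.7% of trials, and the 52-week restricted mean reversed slightly (37.88 censored vs 38.16 event).

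A single small sample can also reverse. Take PD at weeks 10, 12, 20 and 30, and one death at week 17 last scanned at week 9. With death as an event, survival is 0.8, 0.6 and 0.4 at weeks 10, 12 and 17, so the median is 17. With the death censored at week 9, it is 0.75 and 0.50 at weeks 10 and 12, so the median is 12 (16 if the midpoint of 12 and 20 is taken).

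**The case against.** The strongest reply is that PD-only DOR is a deliberate and consistent definition. Both documents end DOR at PD or recurrence, in line with an endpoint described as per RECIST v1.1. Under independent hazards the PD-only Kaplan-Meier curve estimates its own target correctly. That stands: the ratios above are a gap between two estimands, not demonstrated bias. A reader might infer that the censoring is informative. That is plausible, but the documents hold no evidence on how death and PD are related in responders.

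A second reply is that such deaths may be rare, because treatment and scans continue to progression, there is an end-of-treatment scan, and Part 2B patients who stop for other reasons go on being scanned. That also stands, and f may be zero. It does not remove the need for a rule.

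A reader might also infer that PFS has the same gap, because its next sentence says "Patients without a documented event of progression will be censored on the date of their last adequate tumor assessment", which read literally would censor deaths without documented PD. The documents do not support that. SAP Table 1 and the first sentence of SAP 12.2.1 both make death a PFS event, so the censoring sentence is only loosely worded.

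Finally, counting every death could stretch DOR to deaths long after the last scan. In Part 2B, scans stop at subsequent treatment while survival follow-up continues. This is a fair point, and the change needs a rule for it.

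**Conclusion.** The point holds as a definition worth changing. Followed as written, the DOR text most naturally places a responder's death without documented PD among the censored. That this means censoring is an inference from the reporting categories, not an explicit statement.

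If such deaths occur, the Kaplan-Meier median DOR is generally, though not in every sample, longer than the median time to PD or death: by about 5% to 18% for f between 5% and 15% under constant hazards, and not at all if f is zero. Both f and the median are assumptions. The stronger reading, that the reported DOR will be materially inflated, is not supported. DOR is secondary and descriptive, and neither the response rate nor the sample size depends on it.

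**What to change.** Make the change in the SAP and describe and justify there the departure from protocol 11.2.4.2.4, as protocol 11.2.1 allows.

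1. In SAP 12.2.2, define DOR for confirmed responders as time from first response to first RECIST PD or death from any cause, whichever is first. This matches the PFS event in SAP Table 1 and 12.2.1.
2. Censor patients alive without PD at the last adequate tumor assessment.
3. State one rule, the same for DOR and PFS, for deaths after the start of subsequent anticancer therapy; for example, censor at the last adequate assessment before that therapy.
4. Report PD events, deaths and censored patients separately.
5. Keep PD-only DOR as a sensitivity analysis.
6. As an editorial alignment only, reword the PFS censoring sentence in SAP 12.2.1 so that it applies to patients without documented progression or death.

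The cost is a few sentences and no new data collection. Deaths within 28 days of the last dose are already reported as serious adverse events (protocol 10.2), and Part 2B patients are followed for survival and subsequent treatment every 12 weeks (protocol 9.9). The downsides are that DOR may read slightly shorter, and that deaths more than 28 days after the last dose are captured systematically in Part 2B but not in Part 2A. The two cohorts' DOR figures would therefore not rest on equal ascertainment of death, and the report should say so.

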### 12.2.3 Overall Survival (Part 2B)

Overall survival is defined as 1+ the number of days from the date of first dose of study drug to death, due to any cause. Patients without a documented event of death will be censored on the date of their last visit. Overall survival will be summarized using Kaplan-Meier methodology time from randomization until death from any cause and is measured in the intent-to-treat population.

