- ^u = PK samples to be collected predose (any time on Day -7 and Day 1; 5–10 min prior to dosing on Day 15) and at 15 (± 2) min, 30 (± 3) min, 1 h (± 5 min), 1.5 h (± 5 min), 2.5 h (± 5 min), 4 h (± 15 min), 6 h (± 15 min), 8 h (± 15 min), 10 h (± 30 min), and 24 h (± 30 min) postdose on Day -7, Day 1 and Day 15 of Cycle 1.
- ^v = PK sample to be collected any time prior to dosing on Days 8 and 22 of Cycle 1, and on Day 1 of Cycles 3-9.

Table 11. Schedule of Assessments - Part 2A and 2B: All Patients							
Procedure^a	Screening	Dosing Period			End of Treatment (After Last Dose)	Follow-up (28 [±3] Days After Last Dose)	Long-term Follow-up
		Cycle 1		Cycles 2 and Beyond			
		Day -30 to Day -1	Day 1^b	Day 15			
Informed Consent	X						
Medical/Oncology History	X						
Physical Examination	X	X	X ^c	X	X		
Height	X						
Weight	X	X	X	X	X		
ECOG Performance Status	X	X		X	X		
Vital Signs ^d	X	X	X	X	X		
Prior/Concomitant Medications	X	X	X	X	X		
12-lead ECG (in Triplicate) ^e	X	X ^s		X ^s	X		
Hematology ^f	X ^g	X	X	X	X		
Serum Chemistry ^h	X ^g	X	X	X	X		
Serum Pregnancy Test ⁱ	X			X	X		
CA-125 Measurement ^j	X	X		X	X		
Urinalysis ^k	X						
Tumor Scans ^l	X			X ^m	X		X ^t
Archival Tumor Tissue ⁿ	(X)				X		
Adverse Events ^o	X	X	X	X	X	X	
Plasma PK Samples			X ^p	X ^q			
Serum AAG Samples ^r			X ^p	X ^q			
Oral Rucaparib Dispensation/Administration		X	X	X			
Part 2B Only: Survival, Subsequent Treatments, and Secondary Malignancy Monitoring							X ^u

BUN = blood urea nitrogen, CT = computer tomography, EOS = end of study, MRI = magnetic resonance imaging, PET = positron emission tomography, SAE = serious adverse event

- ^a = Unless specified, procedure is completed within ± 1 day of scheduled time point and is synchronized with administration day of rucaparib.
- ^b = At Day 1 of Cycle 1, any procedure may be omitted if completed ≤ 3 days earlier during the screening period.
- ^c = Limited/targeted physical exam to be performed on Day 15 of Cycle 1.
- ^d = Vital signs (blood pressure, pulse, and temperature) taken predose on drug administration days, after the patient has been resting for at least 5 min.
- ^e = 12-lead ECGs (in triplicate) (predose, where applicable) will be run for 10 seconds, > 2 min apart, with patient resting for 5 min prior to recording.

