- ^q = PK sample to be collected any time prior to dosing for Cycles 2, 3, 5, 7, and 9. If dosing is held for toxicity or any other reason, PK sample should still be collected at the end of treatment Cycles 1, 2, 4, 6, and 8.
- ^r = Serum AAG sample to be collected on the same day as the PK sample.
- ^s = Part 2A only
- ^t = Part 2B only. For any patient who discontinued from study treatment for reason other than disease progression or death. To be performed within 7 days prior to the start of every 9 weeks of until radiologically confirmed disease progression, death, or initiation of subsequent treatment. Patients who have been on study at least 18 months may decrease the frequency of tumor scans to every 16 (± 14 days) weeks.
- ^u = All Part 2B patients discontinued from treatment, regardless of reason, should be followed for survival, subsequent therapies, and secondary malignancy every 12 weeks (± 7 days) until death, loss to follow-up, withdrawal of consent from study, or study closure, whichever happens first. Follow-up can be performed via the telephone. Diagnosis of any secondary malignancy requires appropriate documentation (i.e., laboratory and/or pathology reports).

Table 12. Schedule of Dosing, Electrocardiograms, and Pharmacokinetic Sampling, for Part 1 and Part 2 Patients

Procedure and Time Points	Part 1 Food-Effect PK Cohort(s) Only		Part 1 All Cohorts (Unless Otherwise Specified)					Part 2 All Patients			
	Cycle 1							Cycles 2+	Cycle 1		Cycles 2+
	Day -8	Day -7	Day -1	Day 1	Day 8	Day 15	Day 22	Day 1 ^a	Day 1	Day 15	Day 1
Oral Rucaparib Administration ^b		X ^c		X ^d	X	X		X	X	X	X
Plasma PK Samples (Any Time Prior to Dosing, if Applicable)		X		X	X		X	X ^e			X
Plasma PK Sample, Predose						X				X	
Plasma PK Samples, Postdose (15 [±2] min, 30 [±3] min, 1 h [±5 min], 1.5 h [±5 min], 2.5 h [±5 min], 4 h [±15 min], 6 h [±15 min], 8 h [±15 min], 10 h [±30 min], and 24 h [±30 min])		X		X		X					
Duplicate Set of Plasma PK Samples for Metabolite Profiling, Predose (Any Time Prior to Dosing)				(X) ^f							
Duplicate Set of Plasma PK Samples for Metabolite Profiling, Postdose (15 [±2] min, 30 [±3] min, 1 h [±5 min], 1.5 h [±5 min], 2.5 h [±5 min], 4 h [±15 min], 6 h [±15 min], 8 h [±15 min], 10 h [±30 min], and 24 h [±30 min])						(X) ^f					
12-Lead ECGs (in Triplicate, >2 min Apart) (Any Time Prior to Dosing)							X	X	X		X ^g

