9.8 Follow-up Visit

The following procedures will be performed at 28 (± 3) days after the last dose of rucaparib:

- AE monitoring (ongoing SAEs and AEs of special interest [AESI] should be followed until resolution, stabilization, or patient is lost to follow-up)

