9.9 Long-term Follow-up

For Part 2B patients only:

- All Part 2B patients discontinued from treatment, regardless of reason, should be followed for survival, subsequent anti-cancer treatments, and secondary malignancy monitoring every 12 weeks [± 7 days] until death, loss to follow-up, withdrawal of consent from study, or study closure, whichever happens first. Follow-up can be performed via the telephone. Diagnosis of any secondary malignancy requires appropriate documentation (i.e., laboratory and/or pathology reports).
- Tumor scans (using the same methodology as was used at screening) for any patient who discontinued from study treatment for reason other than disease progression or death to be performed within 7 days prior to the start of every 9 weeks until radiologically confirmed disease progression, death, or initiation of subsequent treatment. Patients who have been on study at least 18 months may decrease the frequency of tumor scans to every 16 weeks [± 14 days]

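### Part 2B overall survival is censored at an undefined last visit; if that means a clinic visit, the Kaplan-Meier curve and median can only be equal to or lower than with last-known-alive censoring

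*SAP*

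**What the plan says.** SAP 12.2.3 counts overall survival from first dose to death from any cause and gives one censoring rule: "Patients without a documented event of death will be censored on the date of their last visit". Protocol 11.2.4.2.5 has the same sentence. SAP 13.1 refers the reader back to each endpoint's own section for its censoring rule, so nothing elsewhere defines the date.

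The other two time-to-event efficacy endpoints name their data source. Patients without a PFS event are "censored on the date of their last adequate tumor assessment (i.e., radiologic assessment") (SAP 12.2.1). For duration of response: "Any patients with an ongoing response will be censored at the date of the last post-baseline scan" (SAP 12.2.2).

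Protocol 9.7 and 9.8 are headed as visits (end of treatment, then "9.8 Follow-up Visit" at 28 days after the last dose). Section 9.9 is headed as long-term follow-up. It covers every Part 2B patient off treatment, whatever the reason, and adds: "Follow-up can be performed via the telephone". Post-treatment scans are required only "for any patient who discontinued from study treatment for reason other than disease progression or death to be performed within 7 days" of each 9-week interval. Protocol Table 11 gives long-term follow-up its own column, with the row "Part 2B Only: Survival, Subsequent Treatments, and Secondary Malignancy Monitoring", and its footnote says these patients "should be followed for survival, subsequent therapies, and secondary malignancy every 12 weeks".

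SAP section 4 plans the Kaplan-Meier median with a 95% confidence interval and range. The final sentence of SAP 12.2.3 also refers to randomization and to an intent-to-treat population.

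**The concern.** A patient who stops treatment for progression has no scheduled clinic attendance after the 28-day visit, but can be confirmed alive by telephone every 12 weeks for a long time. If only attendance counts as a visit, the same follow-up system supplies deaths in full and supplies no time at risk for survivors. That is not neutral loss of information, because the date on which follow-up ends then depends on whether the patient died.

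Overall survival is a named secondary endpoint for Part 2B. In a single-arm cohort there is no control group carrying the same error. The reported median could be too low, or could be reported as reached when it would not be under last-known-alive censoring. Two programmers could both follow the SAP and report different medians.

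**Working it through.** **No figure to reproduce.** The documents give no median, event count, power or alpha for overall survival. The direction can be shown from the estimator; the size can only be illustrated.

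**Direction.** The Kaplan-Meier estimate is S(t) = Π(1 − dᵢ/nᵢ) over death times up to t, with dᵢ deaths and nᵢ at risk. Compare two rules on the same patients and the same recorded deaths:

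1. Every dᵢ is the same.
2. Moving a survivor's censoring date earlier removes that patient from nᵢ at each death time in between and adds nobody.
3. So nᵢ is equal or smaller, each factor 1 − dᵢ/nᵢ is equal or smaller, and S(t) is equal or lower at every t.
4. The time at which S(t) reaches 0.5 is therefore equal or earlier, and a median that was not reached may become reached.

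A numerical check with 10,000 random data sets of 40 patients, deaths fixed and censoring times moved earlier, gave no exception for the curve or the median.

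**Size, illustration only.** Every time input is an assumption: exponential survival with true median 20 months; treatment median 6 or 8 months; correlation between treatment time and survival 0.5 or 0.8; uniform accrual over 12 months; 400,000 patients per scenario, so that sampling error is negligible. The rules compared are:

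- A, clinic only: last 21-day cycle visit on treatment, otherwise end of treatment plus 28 days.
- B, as A, plus 9-weekly scans in 25% of patients (median 6 months) and each contact in person with probability 30%.
- C, as B, but 30% of patients always attend in person and the rest never do.
- D, last 12-weekly contact.
- E, alive status confirmed at the cut-off.

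Kaplan-Meier medians in months:

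| Minimum follow-up | Correlation, treatment median | A | B | C | D | E |
|---|---|---|---|---|---|---|
| 12 | 0.5, 6 | 13.9 | 16.7 | 15.6 | 18.8 | 19.9 |
| 12 | 0.5, 8 | 15.0 | 17.2 | 16.4 | 19.0 | 20.0 |
| 12 | 0.8, 6 | 14.8 | 17.1 | 16.3 | 19.0 | 20.1 |
| 12 | 0.8, 8 | 15.9 | 17.6 | 17.1 | 19.1 | 20.0 |
| 24 | 0.5, 6 | 16.1 | 19.3 | 17.4 | 20.0 | 20.0 |
| 24 | 0.5, 8 | 16.9 | 19.4 | 17.9 | 20.0 | 20.0 |
| 24 | 0.8, 6 | 17.0 | 19.4 | 18.0 | 20.0 | 20.0 |
| 24 | 0.8, 8 | 17.9 | 19.6 | 18.7 | 20.0 | 20.0 |

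Gaps read from the table:

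- D − B or D − C: from 19.1 − 17.6 = 1.5 to 18.8 − 15.6 = 3.2 months at 12 months' minimum follow-up, and from 20.0 − 19.6 = 0.4 to 20.0 − 17.4 = 2.6 at 24.
- D − A, with no clinic attendance after the 28-day visit: roughly 3 to 5 months at 12, and 2.1 to 3.9 at 24.
- E − D, if every contact counts as a visit: about 1 month at 12 and 0.0 at 24.

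Sensitivity: with a true median of 15 months, the gap from D to B or C is 0.5–1.7 months at 12 months' follow-up and 0.1–1.0 at 24. With a true median of 20 and 93% dead (72 months), even rule A is only 0.1–0.6 low.

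A separate run used 40 patients per trial, follow-up of 12–30 months, treatment time independent of survival and no attendance after the 28-day visit. For a true median of 12 months it gave 11.8 under last contact against 9.9–10.4 under last clinic visit; for 18 months, about 17.6 against 12.6–13.6. Gaps were larger still for assumed medians of 24 and 30 months. These settings lean towards a large effect and serve only to show how strongly the answer depends on the inputs.

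**The case against.** The strongest reply is that the adverse reading is only one of two. In Table 11 the three post-treatment columns (end of treatment, follow-up, long-term follow-up) are parallel and none is labelled a visit. Telephone contact is permitted, not required. The 12-weekly follow-up exists partly to measure survival, so a reading that discards its alive dates is strained, and the case report form may record each contact as a visit. This stands. A reader might infer that the plan definitely throws away the telephone follow-up; the documents do not say that. They simply do not settle it.

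Second, the month figures rest wholly on assumed inputs, and the simulation has no missed contacts, loss to follow-up or withdrawal, which favours a larger gap. It also leaves out treatment beyond progression (protocol 7.4.4), which would keep some progressed patients attending clinic. This stands too: no particular number of months can be attributed to the plan.

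Third, the shortfall of about 1 month that remains when contacts count as visits comes from 12-weekly spacing and affects any last-contact rule. It is not evidence about the word visit.

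Fourth, the endpoint is descriptive and imprecise. With a 20-month exponential median, about 46% of patients die by 12 months' minimum follow-up and 64% by 24, or roughly 18 and 26 of 40. An approximate 95% interval is 20 × exp(±1.96/√d): 12.6 to 31.7 months for d = 18, and 13.6 to 29.4 for d = 26. The 0.4 to 3.2 month gap under rules B and C lies well inside. That limits the weight of the point but does not remove it: the shift is one-directional and avoidable, and it moves the interval along with the median.

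**Conclusion.** The point holds in conditional form. The censoring date is undefined. If it is read as a clinic visit, the Kaplan-Meier curve and median for Part 2B overall survival can only be equal to or lower than under last-known-alive censoring of the same data. That direction is certain given the same recorded deaths. If survival contacts count as visits, the effect largely disappears.

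The size cannot be derived from the documents. Under the assumed inputs it runs from about 0 to several months, depending on how many patients attend after treatment and how mature the data are; it is small once most patients have died. Neither document sets a required maturity for this analysis.

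Three stronger inferences are not supported: that the plan certainly biases the median, that the bias has a known size, or that it touches the main result. Response rate is unaffected, there is no survival hypothesis, and any error understates survival, so it cannot flatter the drug. This is a wording defect with a possible numerical consequence, and worth correcting before the analysis.

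The randomization and intent-to-treat wording in the same paragraph is a separate error, since Part 2B is not randomized and SAP section 5 defines no such population. It does not add weight to the censoring point.

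**What to change.** Replace the censoring sentence in SAP 12.2.3 with, for example: *For patients with no recorded death up to the analysis data cut-off (state the date), overall survival is censored at the last date known alive from any source, including telephone survival contacts, or at that cut-off if a later contact shows that the patient was alive then.*

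The cut-off date must be written into the SAP, because neither document defines one; SAP section 7 mentions only a database snapshot. The second clause also deals with the small shortfall that contact spacing leaves under last-contact censoring.

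In the same paragraph, delete the closing words that start the clock at randomization and assign the analysis to an intent-to-treat population, and name the safety (all-treated) population. The first-dose origin is already stated and needs no change. Record the new rule as a deviation from protocol 11.2.4.2.5, which protocol 11.2.1 allows the SAP to do.

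Cost: one SAP paragraph and a deviation note. The 12-weekly contacts are already scheduled, so no new data collection is needed, and no protocol amendment is needed for this alone.
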